11.7.1.1.1 Early Safety Review Plan

The DSMB will review safety data after the first 8 participants (n=4/group) have completed the five day dosing period and lab safety data through day 16. It is expected that 8 will be enrolled on each arm at this time point, and 6 will have received 5 days of study product. Upon completion of the review, the board will make a recommendation to either continue the study at the 100-mg GS-5734 dose or reduce the dose to 75 mg for the remainder of the study. If the DSMB finds that a large proportion of participants on the active arm are meeting the criteria for de-escalation of dose, the DSMB should consider recommending the dose be reduced for all participants. As a guideline, if 4 or more of this first set of participants (4 through day 16; 6 through dosing; 8 enrolled) on the active arm have met the criteria for dose de-escalation or experienced grade 1 or higher elevations in AST or ALT, a de-escalation for the remainder of the study would be appropriate. Table 10 shows recommended thresholds for the DSMB decision to recommend study dose de-escalation, based on an assumed enrollment of 2/group (94 total) per week for the first 4 weeks, followed by 4 per group (8 total) on subsequent weeks. The table gives guidelines for DSMB meetings starting at approximately day 23, when 16-day follow-up data on the first 4 people per group should be available, and meeting every two weeks up to the point where there is at least 16-day follow-up available on approximately 50% of the study participants. At the last study point listed below, approximately study week 8, we estimate 48 of 60 participants will be enrolled. Under the assumptions used here, we would expect all participants to be enrolled within two weeks of this time-point, so it is unlikely that study-wide dose de-escalation at time points after this would be suggested.

		Number	Number	Number of S	5	Number of	5
Approx	Number	of with	of with	meet dose de	e-escalation	with Grade	2 or higher
study	of	5 days	16 days	criteria OR	grade 1 or	AST of	r ALT
day	enrolled,	dosing,	follow-	higher AS	T or ALT		
(week)	per arm	per arm	up, per	Treatment	Placebo	Treatment	Placebo
		per ann	arm	Arm	Arm	Arm	Arm
23 (4)	8	6	4	≥4	0	≥1	0
37 (6)	16	12	8	≥ 5	0	≥1	0
51 (8)	24	20	16	≥6	0	≥2	0
65 (10)	30	28	24	N/A	N/A	N/A	N/A

Table 10. Suggested guidelines for dose de-escalation by the DSMB.

Assumes enrollment of 2 subjects on active drug/week enrolled weeks 1-4 in each group, then 4/week

12 Site Monitoring Plan

According to the International Conference on Harmonization Good Clinical Practice (ICH GCP) guidelines, Section 5.18, and FDA 21 CFR 312.50, clinical protocols are required to be adequately monitored by the study sponsor. This study monitoring will be conducted according to the "NIAID Intramural Clinical Monitoring Guidelines." Monitors under contract to the NIAID/OCRPRO will visit the clinical research site to monitor aspects of the study in accordance with the appropriate regulations and the approved protocol. The objectives of a monitoring visit will be: 1) to verify the existence of signed informed consent documents and documentation of the consent process for each monitored subject; 2) to verify the prompt and accurate recording of all monitored data points, and prompt reporting of all SAEs; 3) to compare abstracted information with individual subjects' records and source documents (subjects' charts, laboratory analyses and test results, physicians' progress notes, nurses' notes, and any other relevant original subject information); and 4) to help ensure investigators are in compliance with the protocol. The monitors also will inspect the clinical site regulatory files to ensure that regulatory requirements (Office for Human Research Protections [OHRP]), FDA, and applicable guidelines (ICH GCP) are being followed. During the monitoring visits, the investigator (and/or designee) and other study personnel will be available to discuss the study progress and monitoring visit.

The investigator (and/or designee) will make study documents (e.g, consent forms) and pertinent hospital or clinical records readily available for inspection by the IRBs, the FDA, the site monitors, and the NIAID staff, or other designees, for confirmation of the study data.

A specific protocol monitoring plan will be discussed with the principal investigator and study staff prior to enrollment. The plan will outline the frequency of monitoring visits based on such factors as study enrollment, data collection status, and regulatory obligations.

13 Statistical Considerations

13.1 Study Hypotheses

13.1.1 Treatment Phase

Male survivors of EVD who receive 5 days of IV GS-5734 will have Ebola virus RNA detected in a lower proportion of samples over the first 28 days, as compared to those who receive placebo.

13.1.2 Follow-up Phase

Male survivors of EVD who receive 5 days of IV GS-5734 will have Ebola virus RNA detected in a lower proportion of samples over the first 24 weeks, as compared to those who receive placebo.

13.2 Study Design

This study will use a parallel groups design.

13.2.1 Stratification and Randomization

All participants must have at least two semen samples before enrollment, at least one of which has detectable Ebola virus RNA, in order to be eligible for this study. Subjects will be stratified based on whether screening samples both had detectable Ebola virus RNA, or only one of the two had detectable Ebola virus RNA. Recruitment will focus on PREVAIL III participants with evidence of repeated samples with detectable Ebola virus RNA or CT values <39 on a single sample to try to enroll people likely to have detectable RNA on two screening samples, but participants may be enrolled from outside of PREVAIL III as well. Subjects will also be stratified based on the country in which they reside. There are substantial differences between countries in how the epidemic unfolded and how those with EVD were treated.

Subjects will be randomized 1:1 within the strata defined above.

13.3 Sample Size Justification

Preliminary data from PREVAIL III was used to estimate the rates of detectable virus in semen of survivors. Among 134 men who contributed at least two semen samples, we analyzed the last two semen samples per person. One hundred men had undetectable CT at both time points, 13 (10%) were detectable at both time points, and 21 (16%) had mixed detectability (detectable/undetectable or undetectable/detectable). Based on these estimates, 26% of male survivors may be eligible for the study.

We use this data to estimate the proportion of men who might be eligible for the study as well as the "success" rate among placebos. The enrollment is limited by the number of available subjects with detectable Ebola virus in semen at screening. Based on semen testing in PREVAIL III, approximately 26% of male survivors will have detectable seminal Ebola viral RNA when tested longitudinally during the first 1-2 year window. This percentage may decrease with time.

Based on the power calculations below, complete data on 50 men (25/arm) should be adequate to find a difference under many assumptions. However, as the power calculations do not take into account missing data, nor is it clear what type of heterogeneity or treatment effect might be more realistic, the study will attempt to enroll at least 60 people (30/group), with a target of at least 20 participants with two screening samples with a detectable CT or at least 30 participants have an Ebola NP or GP CT value using the Cepheid of <39. If the total sample size of 60 is enrolled without 20 people with two detectable samples, or at least 30 participants with an Ebola NP or GP CT value using the Cepheid of <39 we will continue to enroll until one of these criteria is met up to a total of 120 people if possible.

13.3.1 Power Calculations

The table below lists the simulated power to find a significant difference in treatment-phase ANR and follow-up ANR for various true rates of ANR in the placebo and GS-5734 arms. With 50 people (25/arm), we will have reasonable power (>80%) to find a difference in both the treatment-phase ANR and the follow-up ANR if the effect of treatment is to cut the probability of a detectable sample by 50% for each person at each time, starting at day 3. If the effect of treatment is instead that 40% of people experience sterilization starting on day 3, such that their probability of a detectable sample drops to 0 (except for false positives), and the rest of the people are unaffected, then the power varies depending on the amount of heterogeneity in the probabilities.

ANR p-value based on t-test on proportion negative at 6 (day 3 to day 28) or 5 (week 8 to week 24) visits. All power estimates based on 1,000 simulations, 1% false positive rate, and 5% false negative rate, alpha=.05, no adjustments for multiple comparisons.

Ν	P _i =P(detectable person i) Control group	Treatment Effect	Power d3- d28 ANR	Power w8- w24 ANR
50	pi=.5	.5	.96	.98
	p _i ~Beta(10,10)	(multiplicative on probability)	.93	.97
	$p_i \sim U(0,1)$	starting d5	.95	.98
	$p_i = \begin{cases} . \ 1 \ with \ 50\% \ chance \\ . \ 9 \ with \ 50\% \ chance \end{cases}$.97	.99
50	p _i =.5	.4	.77	.84
	pi~Beta(10,10)	(Probability sterilize)	.85	.89
	$p_i {\sim} U(0,\!1)$	starting d5	.16	.23

Table 11	. Power	for	endpoints	under	varying	assumptions.
----------	---------	-----	-----------	-------	---------	--------------

		Р	REVAIL IV
		,	Version 10.0
		1	3 May 2019
$p_i = \begin{cases} . \ 1 \ with \ 50\% \ chance \\ . \ 9 \ with \ 50\% \ chance \end{cases}$.52	.67	

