13.4 Statistical Analyses

The primary analysis of treatment-period ANR will be conducted once subjects have completed their 28-day follow up and reviewed by the DSMB. The follow-up ANR can be conducted once all subjects have completed the week 24 visit. ANR will be computed as the proportion of assays in a specified window that are negative. For the primary analysis, any returned CT value will be considered a positive PCR.

The primary analysis will be based on an Intention-to-Treat framework, in which participants are analyzed in the group to which they are randomized, including participants who reduce or discontinue their individual dosing. In the event that the DSMB recommends a study-wide dose reduction, the primary analysis will remain all people randomized to treatment, regardless of dose, compared to all people randomized to control, but the DSMB can recommend increasing the sample size at that point so there are sufficient people at the lower dose for secondary analyses.

The primary analyses of ANR during the treatment phase and during the follow-up phase will be based on a two-sided permutation test comparing the groups (i.e. using a 2 sample t-test to define the test but use its permutation distribution to compute significance). This will be stratified by number of detectable samples during screening and country, as was done for randomization. No multiplicity adjustment will be imposed on the primary analyses of the ANR from the two different time periods.

As the expectation is that the study will be fully enrolled before we have sufficient data collected on the follow-up phase, there are no formal stopping rules for efficacy or futility.

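### Table 11 cannot be reproduced from its printed inputs: the sterilisation rows are wrong, two halving rows need an unstated screening condition, and the onset day conflicts with the text

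*Combined protocol and SAP*

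**What the plan says.** Section 13.3 concludes that "complete data on 50 men (25/arm) should be adequate to find a difference under many assumptions". It adds that missing data are ignored and that the realistic heterogeneity and type of effect are unclear, and so plans at least 60 men and up to 120.

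Section 13.3.1 supports this with Table 11. The text states that "With 50 people (25/arm), we will have reasonable power (>80%) to find a difference in both the treatment-phase ANR and the follow-up ANR", on one condition: that treatment would "cut the probability of a detectable sample by 50% for each person at each time, starting at day 3". For the second effect, 40% of men are sterilised "starting on day 3, such that their probability of a detectable sample drops to 0" apart from false positives. The text claims no 80% there and says that power depends on heterogeneity.

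On method: "ANR p-value based on t-test on proportion negative at 6" visits (treatment) or 5 visits (follow-up), and "All power estimates based on 1,000 simulations, 1% false positive rate, and 5% false negative rate, alpha=.05, no adjustments for multiple comparisons". Table 11 does not state sidedness; Section 13.4 plans a "two-sided permutation test comparing the groups", stratified by number of detectable screening samples and by country.

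Printed power, treatment phase/follow-up, N=50:

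| p_i in control group | Halving | 40% sterilised |
|---|---|---|
| .5 | .96/.98 | .77/.84 |
| Beta(10,10) | .93/.97 | .85/.89 |
| U(0,1) | .95/.98 | .16/.23 |
| .1 or .9, equal chance | .97/.99 | .52/.67 |

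Both blocks of the table start the effect at d5, whereas the text says day 3. Sections 4.3 and 13.2.1 admit only men with at least one of two screening samples detectable. Section 13.3.1 does not say whether the simulated men were selected that way.

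**The concern.** Two patterns in the table look wrong. Under halving, the most heterogeneous row (.1/.9) has the highest power, although all four distributions share a mean of .5 and between-man spread adds variance. Under sterilisation, Beta(10,10) beats constant p=.5, and U(0,1) falls far below the mixture, which has about twice its variance.

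Section 13.3 rests the adequacy of 50 men on this table. If the figures are wrong, a null result could be over-read, above all if the drug clears virus in only some men.

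**Working it through.** **Inputs.** 25 per arm, alpha .05, 1% false positives, 5% false negatives, 6 or 5 visits (Section 13.3.1); two-sided test (Section 13.4). Each man's p_i is drawn once and held over visits.

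**Step 1: hand check of follow-up, p_i as printed.** Follow-up does not depend on the onset day.

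- Observed positive probability: q = .95p + .01(1−p) = .01 + .94p, with mean .48.
- Variance of a man's ANR over 5 visits: .8·Var(q) + q̄(1−q̄)/5.
- Var(p) by row: 0; .25/21 = .0119; 1/12 = .0833; .16.
- Control variance, .8·.94²·Var(p) + .48·.52/5: .0499, .0583, .1088, .1630.
- Halving: treated mean .01 + .47·.5 = .245, difference .235. Treated variance, .8·.47²·Var(p) + .245·.755/5: .0370, .0391, .0517, .0653.
- Sterilisation: treated mean .6·.48 + .4·.01 = .292, difference .188. Treated Var(q) = .6·.94²·Var(p) + .24·.47². Treated variance, .8 times that + .292·.708/5: .0838, .0888, .1191, .1516.
- z = difference/√((V_control + V_treated)/25); power ≈ Φ(z − 1.96).

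| p_i | Halving z, power [table] | Sterilisation z, power [table] |
|---|---|---|
| .5 | 3.99, .98 [.98] | 2.57, .73 [.84] |
| Beta(10,10) | 3.76, .96 [.97] | 2.45, .69 [.89] |
| U(0,1) | 2.93, .83 [.98] | 1.97, .50 [.23] |
| .1/.9 | 2.46, .69 [.99] | 1.68, .39 [.67] |

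The first two halving rows reproduce; the other six cells do not. On this reading the mean difference is the same in every row of a block, so power must fall down the rows. The printed sterilisation column rises twice.

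**Step 2: simulation, treatment phase/follow-up.** Onset at d5, so the first of the six treatment-phase samples is unaffected. Selection means at least one of two detectable screens.

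| p_i | Halving, as printed | Halving, selected | Sterilised, as printed | Sterilised, selected |
|---|---|---|---|---|
| .5 | .94/.97 | .93/.97 | .64/.70 | .64/.69 |
| Beta(10,10) | .90/.96 | .92/.97 | .59/.66 | .60/.67 |
| U(0,1) | .68/.81 | .89/.96 | .41/.48 | .58/.67 |
| .1/.9 | .51/.67 | .94/.98 | .28/.37 | .65/.73 |

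- *Halving.* Selection removes most low shedders: mean p rises to .62 for U(0,1) and .77 for the mixture. All eight cells then exceed .80, within about 6 points of the table. Adjusting for the screening stratum gives .91/.97 and .97/.99 in the last two rows.
- *Sterilisation.* Selection does not rescue this block. Starting the effect at the first visit lifts the p=.5 treatment-phase cell to about .75, near the printed .77, but follow-up stays near .70 against .84. With 1,000 simulations the standard error at .84 is √(.84·.16/1000) = .012, so that gap of .14 is about 12 standard errors.
- *Other settings.* A one-sided test with no assay error and selection gives .79/.84 at p=.5, close to the table, but .76/.81, .71/.79 and .78/.85 in the other rows. Fifty per arm without selection gives .51/.65 for the mixture, near .52/.67, but .91/.94 at p=.5. No single setting reproduces the block.

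**Step 3: heterogeneity from the plan's own data.** Section 13.3 reports 134 men: 100 never, 21 once and 13 twice detectable. Mean p = (21 + 2·13)/268 = .175 and E[p²] = 13/134 = .097. ICC = (.097 − .175²)/(.175·.825) ≈ .46, giving a beta distribution with a ≈ .21, b ≈ .98. Selected on at least one of two detectable, mean p is about .50 and variance about .078, close to an unselected U(0,1) (.083).

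With the stratum-adjusted test at N=50 and onset at d5:

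- Halving: treatment phase about .70 to .77 (the lower end applies the assay error to screening samples too); follow-up .83 to .88. With the effect present from the first visit, treatment phase is .87 to .90.
- Sterilisation: about .44 to .46 and .54.
- At N=60, ignoring assay error at screening: halving .83 to .84 and .92 to .93; sterilisation .53 and .61 to .62.

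**Step 4: onset.** The first on-study semen sample is at day 4 (Section 3.2.1.1). Onset at day 3 means all six samples are affected; onset at d5 means five are. Step 3 shows that this alone can move treatment-phase halving power across 80%.

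**The case against.** The strongest defence is that the trial enrols selected men. Once the inclusion rule is applied, p_i fixed per man gives more than 80% in every halving row for both endpoints, and the stratum-adjusted version is closer still to the printed values. The sentence about 80% is tied to halving only. The plan makes no such claim for sterilisation, prints values as low as .16, admits that the heterogeneity is unknown, and sets 60 men as the minimum.

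Most of that stands. A reader might infer that the claim of more than 80% is simply wrong, or that the code redrew p_i at every visit. The documents support neither: selection with p_i fixed per man comes close to the same rows, and the comparison of rows at equal mean difference no longer applies after selection.

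Three things remain. The selection is nowhere stated in Section 13.3.1, and the table's column presents p_i as the control-group distribution. Selected U(0,1) and mixture populations would have about 46% and 63% of men with two detectable screens, against 13/34 = 38% in the PREVAIL III counts. And the same selection leaves the sterilisation block unexplained, including the p=.5 row, where men do not differ at all.

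**Conclusion.** The point holds in three parts.

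1. The sterilisation rows are wrong as a set under either reading of p_i and either onset. The printed follow-up values .84 and .89 are unsupported, .16/.23 is far too low, and Beta(10,10) should not beat constant p=.5. For enrolled men at 25 per arm, power is below 80%, roughly .4 to .75 (up to about .78 for the stratum-adjusted mixture).
2. The U(0,1) and mixture halving rows match approximately only with an unstated condition on screening. The 80% claim holds for the printed distributions under that condition. Under PREVAIL III heterogeneity with d5 onset, treatment-phase power at N=50 is about .70 to .77; it passes .80 if the effect is present at the first visit.
3. Text and table give different onset days.

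These are misstated power figures beneath the statement that 50 men suffice, not clerical slips. They do not show that the planned 60 to 120 men are too few. The results assume a two-sided test, no missing samples, d5 onset leaving only the first sample unaffected, and, in the Step 2 selected runs, the same assay error at screening as on study.

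**What to change.** Re-run the simulation with p_i drawn once per man, and state in Section 13.3.1 whether p_i is conditioned on at least one of two detectable screening samples. Use one onset day in the text and in Table 11. Replace the sterilisation rows. Restate power for both endpoints under heterogeneity fitted to the PREVAIL III counts, using the stratified test of Section 13.4, at 50 and at 60 men. Tie the 80% sentence to its conditions and say that power for the sterilisation mechanism is below 80% at 25 per arm.

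The cost is a short re-run, an amended Section 13.3.1 and less favourable stated power. No extra participants are needed, and the analysis does not change.

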13.4 Statistical Analyses

The primary analysis of treatment-period ANR will be conducted once subjects have completed their 28-day follow up and reviewed by the DSMB. The follow-up ANR can be conducted once all subjects have completed the week 24 visit. ANR will be computed as the proportion of assays in a specified window that are negative. For the primary analysis, any returned CT value will be considered a positive PCR.

The primary analysis will be based on an Intention-to-Treat framework, in which participants are analyzed in the group to which they are randomized, including participants who reduce or discontinue their individual dosing. In the event that the DSMB recommends a study-wide dose reduction, the primary analysis will remain all people randomized to treatment, regardless of dose, compared to all people randomized to control, but the DSMB can recommend increasing the sample size at that point so there are sufficient people at the lower dose for secondary analyses.

The primary analyses of ANR during the treatment phase and during the follow-up phase will be based on a two-sided permutation test comparing the groups (i.e. using a 2 sample t-test to define the test but use its permutation distribution to compute significance). This will be stratified by number of detectable samples during screening and country, as was done for randomization. No multiplicity adjustment will be imposed on the primary analyses of the ANR from the two different time periods.

As the expectation is that the study will be fully enrolled before we have sufficient data collected on the follow-up phase, there are no formal stopping rules for efficacy or futility.

This study could generate considerable missing data as a consequence of the dose de-escalation plan and unsuccessful donations at individual visits. If there is substantial missingness (more than just a few) then the previous analysis will need to adjust for differences in the number of observations among participants as the proportions from different participants will have different variances under the null hypothesis. This will be accomplished by replacing the 2 sample t-test with a t-test of the regression coefficient associated with an indicator variable for group membership (i.e. active or placebo) from a weighted linear regression analysis with weights given by the number of study visits for which a participant successfully made a donation (these weights are a consequence of inverse relationship between the variance of a binomial proportion and the number of trials).

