5.3 Randomization Procedures

Once eligibility has been confirmed, subjects will be eligible for randomization. Prior to or during the day 1 visit, the investigator or designee will randomize the subject. Subjects will be assigned a unique subject number and randomized in a 1:1 ratio to GS-5734 or placebo. For subjects participating in PREVAIL III, the PREVAIL III subject number will also be used for this study.

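### Section 13.4 does not say whether the permuted ANR statistic is stratum-adjusted, and no block size is stated; adjusting it is a free, small gain in power.

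*Combined protocol and SAP*

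**What the plan says.** Section 13.4 specifies a "two-sided permutation test comparing the groups" for treatment-phase and follow-up ANR, built by "using a 2 sample t-test to define the test but use its permutation distribution to compute significance". The next sentence reads "This will be stratified by number of detectable samples during screening and country, as was done for randomization". Its subject could be the permutation alone or the whole test, statistic included.

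If more than a little data is missing, the same section replaces the t statistic with "a t-test of the regression coefficient associated with an indicator variable for group membership", from a regression weighted by the number of visits with a donation. No stratum term is mentioned there.

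On allocation, Section 13.2.1 says "Subjects will be randomized 1:1 within the strata defined above", and Section 5.3 says men are "randomized in a 1:1 ratio to GS-5734 or placebo". Neither gives a block size or another method of restricting the allocation. Section 13.4 names no effect estimate for the primary analysis and does not define how the two-sided p-value is formed.

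**The concern.** On the literal reading, the strata enter only through the permutation and the permuted quantity is a raw comparison of arm means. If one arm happens to hold more men with two positive screening samples, that imbalance sits in the raw difference. The within-strata permutation distribution is then centred away from zero, and comparing absolute values of t across it wastes power.

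Two things are at stake. Two statisticians could compute different primary p-values from the same data, depending on how they read one sentence. And some precision that the strata offer may go unused in a trial whose enrolment is limited by the number of eligible men (Section 13.3). Validity is not at stake.

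**Working it through.** **Inputs from the plan.** Table 11 uses "alpha=.05, no adjustments for multiple comparisons", 25 men per arm, a 1% false-positive rate and a 5% false-negative rate (Section 13.3.1). Planned enrolment is at least 60 (Section 13.3). Of the men in the Section 13.3 data, 13 were positive twice and 21 once, so the two-positive stratum is 13/34 = 38% of eligible men. Section 1.1 reports 34 men enrolled in Liberia.

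**Assumed.** Block size, a 34/26 country split of 60 men, effects other than halving, the share of missing donations, and how prognostic the strata are.

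**1. The plan's own figure.** Table 11, first row, weeks 8 to 24, gives .98. The detection rate on placebo is 0.5×0.95 + 0.5×0.01 = 0.48. On active it is 0.25×0.95 + 0.75×0.01 = 0.245. The difference is 0.235. With 5 visits, the standard error is √[(0.48×0.52/5 + 0.245×0.755/5)/25] = 0.059, so z = 3.99 and power is about Φ(3.99 − 1.96) = 0.979. This agrees with the table. Not every row of Table 11 reproduced, but all are described as plain t-tests without strata, so none bears on this point.

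**2. What within-strata permutation does to a plain t.** In stratum s let n1s and n0s be the arm sizes, ns their sum, and d_s the difference in mean ANR. With arm counts fixed, the pooled t is a monotone function of the treated-arm total T. Then

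T − E_perm(T) = Σ_s (n1s·n0s/ns)·d_s.

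This identity was checked numerically (0.22813 on both sides). The right side is the stratum-weighted difference, so between-stratum variance is removed even with a plain t. What remains is the centre of the raw mean difference under permutation,

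Σ_s Ȳ_s·(n1s/n1 − n0s/n0),

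where Ȳ_s is the stratum mean. It is zero when both arms hold the same share of each stratum. Otherwise it shifts the two-sided |t| comparison.

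**3. Normal-theory check.** Take strata explaining 10% of the variance and simple allocation, with 80.0% power for the unstratified test. The literal test then has 80.2% and the adjusted one 84.0%. With exact balance both have 84.0%.

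**4. Simulated power (%), 60 men unless stated.** (a) ignores the strata, (b) is the literal Section 13.4 test, (c) uses a stratum-adjusted statistic. Both (b) and (c) are permuted within strata. Differences were taken before rounding where available.

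| Setting | Allocation | (a) | (b) | (c) | c − b |
|---|---|---|---|---|---|
| A: 6 visits, detection ×0.6, rates fitted to the Section 13.3 counts | unblocked | 72 | 72 | 76 | 4 |
| A | blocks of 4 | – | 77.7 | 78.1 | 0.4 |
| A, detection halved | unblocked | – | 91 | 93 | 2 |
| A, detection halved, 50 men | unblocked | – | 85 | 87 | 2 |
| B: 5 visits, detection ×0.65, uniform rates given screening | unblocked | 73.3 | 73.8 | 75.2 | 1.4 |
| B | blocks of 4 | 74.7 | 78.0 | 78.6 | 0.6 |
| B, country difference 0.2 | unblocked | 71.5 | 73.5 | 76.8 | 3.4 |
| B, country difference 0.2 | blocks of 4 | 74.2 | 79.7 | 80.7 | 1.0 |
| C: 6 visits, uniform rates given at least one positive screen | unblocked | – | 86.2 | 88.2 | 2.0 |
| C | blocks of 4 | – | 89.0 | 89.3 | 0.3 |
| C, 30% missing, weighted fallback | unblocked | – | 85.7 | 87.0 | 1.3 |
| C, 30% missing, weighted fallback | blocks of 4 | – | 88.8 | 89.7 | 0.9 |
| D: strong strata (detection .25 vs .75), ×0.65 | unblocked | 48.8 | 60.3 | 73.9 | 13.6 |
| D | blocks of 4 | 46.4 | 72.9 | 75.6 | 2.7 |
| D | blocks of 8 | 49.4 | 74.0 | 77.2 | 3.2 |

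Monte Carlo standard errors are about 0.6 points for the powers in A and 0.2 to 0.3 points for the paired c − b differences in B. Type I error at a nominal 5% was 4.1% to 4.6% for both permutation versions in A and 3.3% to 5.1% for (b) in the B and D family. Under C with missing data and blocks of 4 it was 4.3% for (b) and 4.2% for (c).

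**The case against.** The stratification sentence in Section 13.4 can fairly be read as covering the statistic. The fallback names the coefficient to be tested and does not exclude other terms. Simple 1:1 allocation run separately in each stratum is the same as unstratified simple randomisation, so stratifying at all suggests some restriction such as blocking. With blocks of 4 the gap in A (0.4 points) is within simulation error. At the plan's own halving of detection, the unblocked loss in A is 2 points. The loss also depends on using |t|: doubling the smaller tail raises the unblocked result in D from 60.3% to 70.4% with the statistic unchanged.

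Most of this stands, and it is why the point is minor. It does not settle the matter. Blocking is a reasonable guess, but the documents do not state it. Section 13.4 expects considerable missing data, which can unbalance strata after perfect allocation. Doubling the tail is not a general remedy: in B it gives 73.3% against 73.8% unblocked, and 76.9% against 78.0% with blocks of 4.

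A reader might go further and infer that stratification adds no power to the primary test unless blocks are tight. The documents and the arithmetic do not support that. The identity in step 2 shows that the permutation itself adjusts for the strata. In B the literal test gains 3.3 to 5.5 points over an unstratified one with blocks of 4, and 0.5 to 1.9 points unblocked. In D the unblocked gain is 60.3 − 48.8 = 11.5 points. Blocks of 8 kept about 70% to 90% of the adjusted statistic's gain in the uniform-rate settings.

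**Conclusion.** The point holds as a minor matter of specification and efficiency. The plan leaves open whether the permuted statistic is stratum-adjusted, and it states no block size. Read literally, the test is valid. Its power falls short of a stratum-adjusted version by about 0 to 1 point if allocation is blocked and about 1 to 4 points if it is not. With strongly prognostic strata the shortfall is larger: roughly 3 points blocked and 14 unblocked in D. These sizes rest on assumed block sizes, effects, missingness and stratum strength. In none of the settings tabulated did the adjusted statistic do worse. Because Table 11 takes no credit for stratification, no stated power figure and no sample size depends on this.

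**What to change.** State in Section 13.4 that the permuted statistic is the arm coefficient from a linear regression of each man's ANR on arm plus the randomisation strata (count of positive screening samples and country), permuted within strata. With one indicator per stratum combination, this is the mean difference weighted by n1s·n0s/ns, and its permutation distribution is centred at zero. Put the same strata terms in the weighted regression used when donations are missing. Report this stratum-adjusted difference with a 95% interval as the primary effect estimate. In the same edit, state the allocation method and block size, if this can be done without compromising the blind, and say how the two-sided p-value is formed.

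The cost is a few sentences. No patients, visits or data are added, and type I error stays controlled.
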